Specific Aim #1: To determine if progesterone +TNP is superior to placebo +TNP for prolonged and 7-day point prevalence of smoking abstinence rates at the end of 8 weeks of treatment and at 1 and 3 month follow-up time points. We will also evaluate the safety and tolerability of progesterone treatment, compared to placebo. Our co-primary outcome measures will be 7-day point prevalence of smoking abstinence and breath CO at the end of treatment and 1- and 3-months after the end of the trial.

Specific Aim #2: To determine if progesterone + TNP treatment, compared to placebo + TNP, improves response inhibitory function, as assessed by the Stroop, The Go/No Go task, and the Digit Symbol Task.

Specific Aim # 3: To determine if progesterone + TNP treatment, compared to placebo + TNP, leads to a greater reduction in cigarette craving and nicotine withdrawal symptoms, as assessed

by the Questionnaire on Smoking Urges-Brief (QSU-B) and the Minnesota Nicotine Withdrawal Scale (MNWS), respectively.

Specific Aim #4: To evaluate with affective changes, as shown on the Positive and Negative Affect Schedule, mediates the effects of progesterone on smoking abstinence.

Exploratory Aim: We will evaluate the degree to which serum estradiol and progesterone levels achieved during the trial are associated with a) greater smoking abstinence, b) improved response inhibition, and c) less craving and withdrawal symptoms.

2. **Background:** Describe the background information that led to the plan for this project. Provide references to support the expectation of obtaining useful scientific data.

Nicotine addiction continues to be the main preventable cause of death in developed countries, with an estimated 435,000 premature deaths in the U.S and 5 million deaths worldwide (11). About 18% of women and 22% of men in the US smoke (11). Some evidence suggests that women respond less favorably to NRTs, even though they maintain their nicotine addiction with lower levels of nicotine intake than men (12-15). Women, compared to men, may be more vulnerable to the complications of smoking, most notably lung cancer (16, 17). In the US, lung cancer kills more women than the breast and colon cancer combined. These findings support the need to develop more effective treatments tailored for female smokers.

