The RA will complete a checklist that indicates eligibility criteria. The checklist will be reviewed by study clinician who will confirm that this information has been gathered and that the participant meets criteria for participation. For women who continue to be eligible, the RA and/or study clinician will ask baseline measures that include: 1) a menstrual history form including module for diagnosis of premenstrual dysphoric disorder and menstrual cycle dating, the Fagerstrom Test for Nicotine Dependence (FTND) (11); the Minnesotal Nicotine Withdrawal Scale (MNWS) (12), the Questionnaire on Smoking Urges-Brief (QSU-B) (13) and the Positive and Negative Affect Schedule(14) . They will also complete the following neurocognitive tasks: 1) the Stroop, (15) 2) Go/No Go, 3) Digit Symbol Substitution Test (part of the WAIS III), 4) The Shipley Institute of Living Scale (SILS) is a paper-and-pencil, self-administered scale that consists of a 40-item vocabulary and a 20-item pattern recognition section (16).

Randomization/Visit 1: After eligibility is confirmed and the baseline assessments are completed, women will be randomized. Women will then begin smoking cessation counseling and will receive two weeks supply of their study medication, TNP + either oral micronized progesterone or placebo. They will be instructed to apply one nicotine patch /day and to take one pill twice daily after the visit. They will be instructed to set a quit date for the 5 (+/-2) days after the onset of menses, ideally around the 3-4th day when perimenstrual symptoms have abated and before estrogen peaks. We will call them at the estimated time of menses onset to confirm dates and quit date plans. We used similar strategies in smoking studies and menstrual cycle studies (6).

Treatment Phase (Visit 2 to 8): Women will be seen for follow up around days 7-11 of their menstrual cycle, shortly after their quit date. This visit will confirm that treatment with TNP + progesterone or placebo was initiated and maintained for the estimated 2 weeks since Visit 1. Medication compliance will be assessed by pill count. Support and counseling will be

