provided for the quit attempt. Assessments will be repeated although the neurocognitive battery will only be done a second time at this first follow up visit. A blood draw will be completed twice throughout the study, the first around Visit #2 and the other around Visit #6 or Visit #7 at a professional lab on the first floor of the research site building. Approximately 6 ccs of blood will be drawn for each.

Other assessments will be conducted weekly for the additional weeks of the study. Assessments will include a weekly calendar of cigarettes smoked, if any, breath CO. We will collect urine for cotinine if the breath test is negative and there are concerns about compliance with TNP. If there is a possibility that a participant is pregnant (i.e. she is not menstruating or in the week following menstruation) we will also test urine for positive pregnancy. Additionally, subjects will have brief behavioral treatment sessions for smoking abstinence.

End of study (Visit 8), Termination and follow-up: At the end of the 8-week treatment period, participants will complete their weekly ratings, collect breath CO. Participants and study staff will be asked to guess their treatment condition (progesterone or placebo) and will discontinue study capsules and TNP. All participants will be encouraged to remain abstinent from smoking (9). Follow-up visits will be scheduled at 1 and 3 months after the end of the study. At follow up, assessments of smoking and the PANAS will be repeated. We will not repeat the neurocognitive measures.

Strategies to minimize attrition and enhance follow up: We will: 1) rapidly assign study treatments after application confirmation of eligibility, 2) thoroughly explain study treatments and requirements, and 3) specify uniform procedures across treatment conditions regarding study staff's handling of participants who miss or come late to sessions. Study investigators will monitor participants who drop out and explore with the staff reasons for the dropouts. We will follow the full randomized sample, regardless of their retention in treatment, by including: 1) a thorough explanation at the consent interview of the importance of follow-ups, 2) collecting at least three verified locators who are likely to have knowledge of a subject's whereabouts, 3) paying participants to cover transportation and parking for follow-up visits.

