Main outcomes are prolonged smoking abstinence (Y/N at each point) and rates of 7-day point prevalence of abstinence(Y/N at each point). Following the recommendations of the Society for Research on Nicotine and Tobacco workgroup, the 7-day point prevalence is defined by self-reported smoking abstinence for the last 7 days, and expired carbon monoxide <10 ppm. Prolonged smoking abstinence is self-reported smoking abstinence starting with a 2-week grace period after the quit day (i.e., last 5 weeks of the treatment phase) without relapse to: the end of the trial, 1 month and 3 months post trial. Relapse is defined by a) smoked for 7 consecutive days or b) smoked at least once each week for 2 consecutive weeks, or c) missed 2 consecutive weekly appointments or 2) failed breath test at any previous outcome assessment. Additional outcomes include measures of withdrawal (MNWS and QSU-B), and response inhibition (Stroop and SST).

Data Analysis: We will follow CONSORT guidelines for the conduct and reporting of the trial. Descriptive statistics will be used to summarize the data on all randomized subjects, although, as per CONSORT, these parameters will not be included in the statistical model for primary analyses. Aim #1: To determine whether progesterone with TNP is superior to placebo and TNP we will use generalized estimating equations (GEE), an autoregressive correlation structure a binomial distribution and either identity or log link. A time-by-treatment interaction will be included in the GEE model. The 8-week period will include a continuous version for the time variable and the follow up periods will treat time as categorical. A GEE model such as this can evaluate whether there is an overall difference between the progesterone and the placebo groups and whether the rate of change in smoking abstinence is different between the two groups. For data that are missing, we will perform inverse weighting to determine if data are missing at random (25). The weight will be the inverse of the probability not dropping out. If there are concerns of informative dropout and/or informative intermittent missing data, which is typical of clinical trial data, we will use

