pattern mixture models (26) and perform sensitivity analyses. In sensitivity analyses, participants who miss visits will be coded as smoking. Exploratory analysis will include plasma estradiol and progesterone levels as covariates in order to determine if they contribute to treatment response and PANAS scores as mediators of response to progesterone or placebo. Secondary analyses (the MNWS QSU-B) will be modelled similarly. The main outcome measures for the Stroop test are throughput and interference score. For the SST, the main outcomes are stop signal reaction time (msec) and go reaction time (msec). We will use hierarchical linear models with each cognitive measure as separate longitudinal outcomes and treatment group assignment as regressors.

**Power:** The sample size of 25 per condition was selected to provide an adequate assessment of feasibility and estimate effect sizes. Nonetheless, we determined what level of power we would have based upon a significance level of  $p < 0.05$ , 2 sided test for 7-day or prolonged abstinence. If rates of abstinence are 0.2 in the TNP only group and 0.4 in the progesterone and TNP group then the power would be 88%. If the rate of abstinence in the treated group is 0.38, power is reduced to 80%. In prior studies with the Stroop and SST, we found effect sizes  $> 0.5$  of progesterone vs placebo. Our sample size would have adequate power ( $> 80\%$ ) to detect a 2-fold difference in response. Clearly, these are large differences between groups but would provide a stable effect size estimate for a larger trial if findings are suggestive of a therapeutic effect of the combination treatment.

**Timeline:** We will use the first 3 months for study set up that will include final human subjects' approval, hiring and training of staff, database set up, computerization of the interview and assessment measures. Recruitment will begin immediately afterward. We will conduct ongoing data cleaning and will prepare reports for the human subjects' board, the DSMB and NCI at regular intervals. The final analysis and study report will occur in the last 3 months of the work period.

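### The cognitive analysis names a stop-signal outcome that no visit collects, leaves two Aim 2 tests without a variable and, read literally, uses a model that halves the treatment effect

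*Combined protocol and SAP*

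**What the plan says.** **Tests planned and scheduled.** Specific Aim #2 (Section V, item 1) assesses response inhibition by the "Stroop, The Go/No Go task, and the Digit Symbol Task". The baseline visit (Section V, item 3, Study Procedures) lists the Stroop, then "2) Go/No Go, 3) Digit Symbol Substitution Test (part of the WAIS III", and the Shipley scale. Under Treatment Phase, "the neurocognitive battery will only be done a second time at this first follow up visit", which is Visit 2. The battery is not given at the 1- and 3-month follow-ups. That makes two occasions in all.

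**Tests analysed.** Section V, item 12 lists among the additional outcomes "response inhibition (Stroop and SST". It defines two Stroop variables (throughput and an interference score) and then states: "For the SST, the main outcomes are stop signal reaction time (msec) and go reaction time (msec".

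**Model.** "We will use hierarchical linear models with each cognitive measure as separate longitudinal outcomes and treatment group assignment as regressors".

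**Purpose of the sample.** The 25 per arm were "selected to provide an adequate assessment of feasibility and estimate effect sizes". The Power paragraph also cites effect sizes above 0.5 from earlier Stroop and SST work.

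**The concern.** There are three gaps. First, stop signal reaction time has no source test, because the SST appears only in item 12. Secondly, Go/No Go and Digit Symbol, two of the three Aim 2 tests, have no named score. Each can yield more than one, so the choice would fall after data collection. Thirdly, the model does not say how the baseline score or time enters. With one pre-treatment and one post-treatment value and only a group term, the coefficient does not estimate the effect of treatment on the later score.

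Response inhibition is the whole of Aim 2. The Innovation section proposes it as the cognitive mediator, and the Exploratory Aim relates hormone levels to "b) improved response inhibition". A pilot meant to yield effect sizes for a larger trial needs a defined variable and a defined contrast.

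**Working it through.** **Step 1. The text side by side.**

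| Place | Stroop | Go/No Go | Digit Symbol | SST |
|---|---|---|---|---|
| Specific Aim #2 | yes | yes | yes | no |
| Baseline visit, repeated once at Visit 2 | yes | yes | yes | no |
| Item 12, variables defined | yes | no | no | yes |

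SST is never spelled out, but stop signal reaction time identifies it. It cannot be a slip for the Digit Symbol test (DSST), which does not give that score. Go reaction time is assigned to the SST, so it does not supply a Go/No Go outcome.

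**Step 2. What the model estimates.** Randomisation makes the expected baseline difference 0. Let the follow-up difference be d. A group-only model over both visits estimates (0 + d)/2 = d/2.

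**Step 3. What the choice of contrast does to power.** The plan states no power figure tied clearly to these outcomes, so there is none to reproduce.

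Inputs:
- 25 per arm (item 12, Power).
- d = 0.5, the lower bound cited there, with SD 1.
- Two-sided 0.05, which the plan states for abstinence and which is assumed here for cognition.
- Complete data (assumed).
- Correlation r between baseline and follow-up of 0.3, 0.5, 0.7 and 0.8 (assumed; the documents give none).

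Power is from the noncentral t with noncentrality D / (S × √(2/25)), where √(2/25) = 0.2828. D is the difference estimated and S its SD:
- Group effect averaged over both visits: D = 0.25, S = √((1+r)/2), df 48.
- Change from baseline: D = 0.5, S = √(2(1−r)), df 48.
- Follow-up only: D = 0.5, S = 1, df 48.
- Baseline-adjusted: D = 0.5, S = √(1−r²), df 47.

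Example at r = 0.5. Averaged: 0.25/(0.866 × 0.2828) = 1.02, power 17%. Change: 0.5/(1 × 0.2828) = 1.77, power 41%. Adjusted: 0.5/(0.866 × 0.2828) = 2.04, power 52%.

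| Analysis | r = 0.3 | 0.5 | 0.7 | 0.8 |
|---|---|---|---|---|
| Averaged over both visits | 19% | 17% | 16% | 15% |
| Change from baseline | 31% | 41% | 61% | 78% |
| Follow-up only | 41% | 41% | 41% | 41% |
| Baseline-adjusted, simple formula | 44% | 52% | 68% | 82% |
| Baseline-adjusted, allowing for chance imbalance | 43% | 51% | 67% | 81% |

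The last row multiplies the variance by 1 + 1/46 for chance baseline imbalance.

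**Step 4. Cost if baseline carries no information (r = 0).** The 95% CI half-width without adjustment is 2.0106 × 0.2828 = 0.569. With adjustment it is 2.0117 × 0.2828 × √(1 + 1/46) = 0.575. Power falls from 41.0% to 40.3%, about 0.7 points.

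**The case against.** **Longitudinal modelling may already include baseline.** With exactly two occasions, calling the outcomes longitudinal most naturally makes baseline one of them, and a time-by-treatment term may be intended. The contrast would then be essentially change from baseline. This stands as a limit on the size of the gain. By the simple formula, adjustment then adds about 7 points at r = 0.7 and 4 at r = 0.8, and more at lower r (13 at r = 0.3). It does not remove the gap. The time-by-treatment term in item 12 belongs to the Aim 1 GEE, and the sentence extending that approach covers only the withdrawal and urge scales.

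**The model sentence covers every cognitive measure.** It may take in Go/No Go and Digit Symbol generically, but it names no score for either.

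**A reader might infer that adjustment would double power, from 41% to 82%.** The documents do not support that. The 41% is for a follow-up-only analysis, which the plan does not state, and 82% needs r = 0.8.

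**A reader might infer that the prior SST effect size is wrong.** The Background reports Stroop and Digit Symbol results, but it is a summary, and the sources cannot be seen here. That the figure cannot be traced does not show an error. Nor is it clear that the power claim for a two-fold difference refers to cognition.

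**A reader might infer that outcomes were left open so as to be chosen on results.** The June 2017 update says that first-cohort progesterone levels by arm were known. It does not say that cognitive scores were compared by arm. This calls for disclosure only.

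**Conclusion.** The concern holds. Followed as written, item 12 calls for an SST outcome that no scheduled test supplies, leaves two of three Aim 2 tests without a variable and, on a literal reading, estimates half the treatment effect. It should be fixed, but it does not threaten the trial: item 12 classes these outcomes as additional, and the abstinence analyses do not depend on them.

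The power figures show how widely the possible readings differ, from about 15% to 82% across the assumed correlations. They rest on the original 25 v 25 design, complete data, d = 0.5 and assumed r. Attrition before Visit 2 would lower them. So would the comparison that the June 2017 update contemplates, of second-cohort active participants against pooled placebo. As an illustration only, assume 10 active against 25 + 2 = 27 placebo: the unadjusted half-width is 0.75 and power at d = 0.5 is 26%.

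**What to change.** 1. Confirm from task records which task was run, and make Specific Aim #2, the baseline task list and item 12 agree. If it was Go/No Go, replace the SST outcomes with named outcomes that this task yields, for example commission-error rate and go reaction time. If it was a stop-signal task, correct Aim 2 and the baseline list. In either case name a Digit Symbol outcome, for example total correct. Do this before any cognitive score is compared by arm, and disclose that it was set after first-cohort hormone levels by arm were known.
2. Replace the model sentence with: *Each first-follow-up cognitive score will be regressed on treatment and that test's baseline score, and the adjusted difference reported with its 95% CI.* An equivalent longitudinal model with time-by-treatment and equal baseline means would also serve.
3. If the SST was not run, keep any prior SST effect size in the Power paragraph only as rationale from a different task.

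The cost is wording, a records check and one covariate per model. In the worst case, an uninformative baseline, that is the 0.7 points of power shown above. Definitions fixed now cannot be called fully prespecified for the first cohort.

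### The stated 88% and 80% power do not follow from 25 women per condition; at a single time point power is about 34% and 28%

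*Combined protocol and SAP*

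**What the plan says.** Section V, item 12 (Statistical Considerations), Power paragraph, gives feasibility as the reason for the sample size: "The sample size of 25 per condition was selected to provide an adequate assessment of feasibility and estimate effect sizes". It then gives power at the 0.05 level for a "2 sided test for 7-day or prolonged abstinence". With 0.2 abstinence in the patch-only group, "0.4 in the progesterone and TNP group then the power would be 88" per cent, and "If the rate of abstinence in the treated group is 0.38, power is reduced to 80" per cent. It names no test, contrast, number of assessments, within-woman correlation or dropout rate. It adds that differences of this size "would provide a stable effect size estimate for a larger trial".

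The same item lists as a main outcome "prolonged smoking abstinence (Y/N at each point"), the points being the end of the trial and 1 and 3 months later, with no relapse up to each. Its Data Analysis paragraph plans a GEE with autoregressive correlation and a time-by-treatment interaction. It gives no correlation value and does not connect the power figures to that model.

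**The concern.** A doubling from 0.20 to 0.40 is hard to detect with 25 women per arm, and 88% is far above what a two-group comparison of that size delivers. The gap would have to come from repeated measures, and the protocol gives none of the quantities needed to show that it does.

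A null result read against 88% power would look like evidence against a doubling of abstinence, when the chance of detecting one at a single time point is about one in three. The estimate meant to inform a larger trial would also be much less precise than the text suggests.

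**Working it through.** **Inputs.** From the Power paragraph: n = 25 per arm, two-sided α = 0.05, control rate 0.20, treated rate 0.40 or 0.38. Allocation is 1:1 (Statement of Purpose).

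**1. Single time point.** Power = Φ[(Δ − 1.96·SE₀)/SE₁], with SE₀ = √[2p̄(1−p̄)/n] and SE₁ = √[(p_C(1−p_C) + p_T(1−p_T))/n].

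- 0.20 vs 0.40: p̄ = 0.30, SE₀ = √(0.42/25) = 0.1296, SE₁ = √(0.40/25) = 0.1265. (0.20 − 0.2540)/0.1265 = −0.427, so power is 0.335 (stated: 0.88).
- 0.20 vs 0.38: p̄ = 0.29, SE₀ = 0.1283, SE₁ = √(0.3956/25) = 0.1258. (0.18 − 0.2515)/0.1258 = −0.569, so power is 0.285 (stated: 0.80).

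Other two-sided methods (0.40 / 0.38):

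| Method | Power |
|---|---|
| Unpooled z | 0.352 / 0.298 |
| Exact chi-square | 0.352 / 0.299 |
| Log link | 0.315 / 0.272 |
| Fisher's exact test | 0.231 / 0.187 |

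A one-sided test gives 0.458 / 0.402, and 50 per arm (two-sided) gives 0.590 / 0.510. None approaches the stated values.

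**2. What would reproduce 88% and 80%.** With n = 100 per arm the same formula gives 0.876 and 0.806. The exact requirements are 102 per arm (88% at 0.40) and 99 per arm (80% at 0.38). With 25 per arm, 80% power needs a treated rate of about 0.58.

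**3. Prolonged abstinence.** Averaging three points with common correlation ρ multiplies the variance by (1 + 2ρ)/3, so the effective n per arm is 75/(1 + 2ρ).

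| ρ | Effective n per arm | Power at 0.40 | Power at 0.38 |
|---|---|---|---|
| 0 | 75 | 0.767 | 0.684 |
| 0.5 | 37.5 | 0.471 | 0.402 |
| 1 | 25 | 0.335 | 0.285 |

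With unpooled variance the ρ = 0 row is 0.782 and 0.698. Zero correlation is impossible here, because being relapse-free to 3 months implies being relapse-free to the two earlier points. If the stated rates held at all three points, the three outcomes would be identical and the last row would apply.

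**4. Repeated 7-day abstinence.** The gain needed is about 4-fold (101.3/25 = 4.05 and 98.6/25 = 3.94). I assumed weekly AR(1) correlation ρ^(weeks apart), the full difference at every measure, no dropout, and the two follow-ups at weeks 12 and 21. The effective n is 25·m²/(1′R1) with equal weights or 25·(1′R⁻¹1) with efficient weights. The highest ρ that still gives 88% / 80% is:

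| Measures | Equal weights | Efficient weights |
|---|---|---|
| Weeks 2–8 (7) | 0.315 / 0.330 | 0.325 / 0.342 |
| Weeks 1–8 (8) | 0.379 / 0.393 | 0.393 / 0.408 |
| Weeks 3–8, 12, 21 (8) | 0.481 / 0.497 | 0.590 / 0.610 |
| Weeks 2–8, 12, 21 (9) | 0.519 / 0.534 | 0.631 / 0.648 |
| Weeks 1–8, 12, 21 (10) | 0.552 / 0.565 | 0.662 / 0.677 |

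The rows that include week 1 are generous. The Treatment Phase text puts Visit 2 about two weeks after Visit 1 and just after the quit date, so a full difference cannot exist in week 1.

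The protocol gives no ρ, so a range is needed. For 0.20 vs 0.40 on the nine-measure schedule, power (equal to efficient weights) is:

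| ρ | Power |
|---|---|
| 0.5 | 0.891–0.931 |
| 0.6 | 0.825–0.895 |
| 0.7 | 0.737–0.839 |
| 0.8 | 0.626–0.745 |
| 0.9 | 0.491–0.582 |

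**5. Precision.** The 95% CI half-width for 0.40 − 0.20 at one time point is 1.96·√[(0.16 + 0.24)/25] = 0.248, giving an expected interval of about −0.05 to 0.45.

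**The case against.** The planned Aim 1 analysis is a GEE, and one of its purposes is an overall group difference, so a single-time-point calculation is not the planned test. Both stated figures imply nearly the same information, about 100 independent observations per arm. Eight weekly AR(1) measures at ρ = 0.4 give 87.6% and 80.6%, very close to both. An undisclosed repeated-measures calculation may therefore lie behind them. Women who relapse are encouraged to set a new quit date, so 7-day status can change and moderate correlations cannot be dismissed. Finally, this is a pilot whose size rests on feasibility, and no design feature depends on the power statement.

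Most of this stands for 7-day abstinence: there the figures are uncheckable, not shown to be impossible. It does not help prolonged abstinence, which the power statement also covers and where nesting removes the gain from repetition. The pilot status explains why the sample size can stay. It does not make a stated power correct, and a reader will still use that figure to interpret the result.

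**Conclusion.** The concern holds. From the stated inputs, power at a single time point is about 34% and 28%, against 88% and 80%: a shortfall of more than 50 percentage points in each case. For prolonged abstinence at its three named points the claim is wrong. The ceiling is about 77% and 68% (78% and 70% unpooled) under a correlation the definition excludes, and power is 34% and 28% if the stated rates hold at all three points.

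For repeated 7-day abstinence the figures cannot be reproduced from what is stated. They need the full difference at every measure, no dropout, and a weekly correlation of at most about 0.4 to 0.7 with 8 to 10 measures, or about 0.32 to 0.34 with seven on-treatment measures. Those limits rest on the AR(1) form and on placing the follow-ups at weeks 12 and 21, which is my assumption. The single-time-point result needs no such assumption. An expected interval from −0.05 to 0.45 does not support calling the effect estimate stable.

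**What to change.** Keep the sample size and its feasibility rationale. Replace the power figures with text such as: *With 25 per condition and a two-sided 5% test at a single time point, power is about 34% for 0.20 vs 0.40 and about 28% for 0.20 vs 0.38; 80% power requires about 0.58 vs 0.20; the expected 95% CI half-width for a 0.40 vs 0.20 difference is about ±0.25.*

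- If a GEE-based power for 7-day abstinence is also quoted, state the contrast, the visits, the within-woman correlation, the assumed effect over time and the dropout, and show a range of correlations.
- Remove the claim of a stable effect size and commit to reporting estimates with 95% confidence intervals.
- Say that these figures describe the original 25 vs 25 comparison, not any comparison using the second cohort added in June 2017 (at least 12 women, 6:1).
- While editing the paragraph, name the endpoint of the sentence claiming more than 80% power "to detect a 2-fold difference in response", which follows the Stroop and SST sentence. Withdraw it if it means 0.20 vs 0.40 abstinence.

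The cost is protocol and SAP wording, with a less favourable stated power. No extra participants are needed.
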